### 2.2 BACKGROUND

This proposal addresses an important unmet clinical need by generating rigorous evidence on the comparative clinical benefits, risks, quality of life and cost-effectiveness of a long-acting insulin analogue vs. intermediate-acting human insulin in low-resource settings. Prior studies conducted in higher income settings are not sufficient because they do not address this specific population(s) of interest and have also not used continuous glucose monitoring (CGM) to capture important glycemic outcomes.

In low-resource or humanitarian settings where glycemic control is typically poor and food insecurity is common, long-acting insulin analogues may offer tangible clinical benefits for patients with T1D. NPH insulin must be dosed at least twice daily in individuals with T1D to ensure 24-hour basal insulin coverage and peaks 4-6 hours after injection, which can lead to hypoglycemia if not eating or overnight. Premixed 70/30 human insulin contains a mix of 70% NPH insulin and 30% short-acting regular insulin, which has been associated with a significant hypoglycemia risk. Glargine has a duration of 24 hours, can be injected once a day, and has a smoother time-action profile. In settings of food insecurity, the pharmacokinetic profile of glargine may reduce the risk of severe hypoglycemic events overnight, which can be fatal. Moreover, it may reduce potential long-term sequelae of recurrent hypoglycemia, such as hypoglycemia unawareness, and may allow for improved glycemic control thereby reducing the risk of long-term complications (e.g., microvascular disease) from diabetes.

Existing efforts to overcome a two-tiered system of global diabetes care (i.e. access to modern, designer insulin analogues in high-income settings, but only human insulins for much of the world's poor) are currently hampered by a lack of hard evidence. Although conclusive evidence for the clinical superiority of insulin analogues in these settings is lacking, many patients and global advocates strongly prefer newer insulins. This is due in part to their added convenience and reduced risk of hypoglycemic events

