## 9 STATISTICAL CONSIDERATIONS

### 9.1 STATISTICAL HYPOTHESES

Null hypothesis: % Time-in-serious hypoglycemia and % Time in Range (TIR) in the insulin glargine group is the same as % Time-in-serious hypoglycemia and % TIR in the control group (usual care with human insulin).

Alternative hypothesis: % Time-in-serious hypoglycemia or % TIR in the insulin glargine group is different than in the control group (usual care with human insulin).

Since this trial has 2 coprimary outcomes, a win on either outcome will be considered to be a positive trial. For example, if insulin glargine “wins” ( $p<0.025$  for benefit) on either the Time-in-serious hypoglycemia OR TIR outcome, it’s considered a positive trial for analogue insulin.

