## 9.2 SAMPLE SIZE DETERMINATION

We estimated power using a bootstrap-resampling approach due to the expected non-standard distribution of the outcome variables (i.e. %time in serious hypoglycemia and %time-in-range). Using individual patient level CGM data collected from a pilot study involving more than 80 children with T1D in Uganda and Kenya (personal communication [name], University of Minnesota), we calculated a mean percent time $<54$  mg/dl of 5.8, standard deviation of 6.6, a maximum of 24. We next assumed a clinically meaningful 33% relative reduction in percent time-in-serious-hypoglycemia (e.g., from a median of 6% to 4%) since clinical guidelines recommend that patients and providers aim for <15 minutes per day (~1%) in hypoglycemia spent at <54 mg/dl. Therefore, in each simulated trial, the simulated patients in the usual-care arm had an outcome drawn from the “control” distribution; the simulated patients in the glargine arm had an outcome drawn from the control distribution multiplied by 0.67 (e.g. corresponding to a 33% relative reduction in time-in-serious-hypoglycemia).

To estimate the study power, we simulated outcomes for control-group (human insulin) and treatment-group (analogue insulin) at sample sizes ranging from 100 up to 400 patients and performed the planned primary analyses described above on the simulated datasets. The power to detect a treatment benefit of glargine insulin is thereby computed as the percentage of simulated trials with a p-value less than 0.025 favoring glargine on each of the respective coprimary outcomes. Since we have 2 coprimary outcomes, an alpha threshold of 0.025 is used for each analysis to control the overall trial-wide type 1 error probability at 0.05. Using this approach, an analytic sample size of 300 patients (150 per arm) would have 77.7% power to detect a treatment benefit corresponding to approximately a 33% relative reduction in time-in-serious-hypoglycemia. If the benefit is larger (e.g. 50% relative reduction) we will have over 99% power to detect a treatment benefit on the hypoglycemia endpoint.

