**Incomplete or missing CGM Sensor Data:** Even though returning a baseline CGM sensor (i.e. the one placed during the run-in phase) is one of the trial eligibility criteria, it is expected that some participants may have incomplete or missing CGM sensor data. For example, a CGM sensor could fall off accidentally before the end of each 14 day sensor wear period. Such sensors may also be lost before study staff have an opportunity to download the glucose data.

If a CGM sensor falls off early, or presents with no data due to a sensor download error, or is accidentally removed less than 9.8 days (70% of 14 days; consistent with international consensus recommendations on the use of CGMs in clinical trials), they may receive a replacement sensor. If a participant is able to successfully wear a sensor for 14 days, but a sensor shuts-off early (e.g. only 6 days of glucose measurement data is captured), they will not have a replacement sensor. Rationale: randomization should balance incomplete sensor data across the two study arms.

In the *primary* analysis, we will include all available sensor data (regardless of the duration of sensor wear or the number of days of glucose measurements) collected while enrolled in the study. In a *sensitivity* analysis, we will include only sensors with at least 70% of data availability during each 14 day wear period (i.e.  $\geq 9.8$  days). In another *sensitivity* analysis, we will impute for missing data. In an exploratory analysis, we will include data from 12-month follow-up replacement sensors that were collected after a participant completed study.

**Lost to follow-up:** If a participant discontinues before any of the follow-up CGM data are recorded (e.g. participant has no recorded CGM data at all during follow-up) they will not contribute data to the primary efficacy analysis. As described above, we are planning the study to have sufficient power with a usable analytic sample of  $n=300$  participants. We propose to recruit  $n=400$  participants, which allows for up to 25% attrition (participants that are lost shortly after randomization, before any CGM data have been collected) while retaining sufficient power to test our primary hypothesis.

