In recognition of the fact that in some cases a participant’s discontinuation could represent a negative clinical outcome, we will perform several sensitivity analyses to ensure that we are thorough and transparent in reporting the possible effects that the missingness would have on our primary analysis. The first sensitivity analysis will be multiple imputation analysis, imputing the missing outcome data based on observed baseline data; this approach is preferred to single-imputation (e.g. last observation carried forward or assign-the-worst) as it takes into account residual uncertainty in the missing values. The second sensitivity analysis will be a win-ratio analysis where participants that died during the study are ranked as having the worst possible outcome; participants that discontinued study participation due to an adverse event are ranked as having the second worst outcome value; participants that discontinued with no known adverse event are ranked as having the third worst outcome value; and participants that return complete CGM data during the intensive follow-up period are ranked according to their % time-in-serious-hypoglycemia ( $<54$  mg/dl), with higher scores representing worse outcomes. This approach provides an estimate of which treatment arm led to better overall outcomes while including death, discontinuation, and hypoglycemia into a single composite outcome measure. This will

not be the primary analysis due in part to difficulty interpreting the results and the emphasis on glycemic control as the most important outcome in this therapeutic trial, but it will provide an important check that any observed benefits on a time-in-serious-hypoglycemia outcome or the time-in-range outcome are not offset or explained by greater death or discontinuation in the other treatment arm.

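### The win-ratio sensitivity analysis cannot test whether a co-primary benefit is explained by greater loss in the other arm, because its ranking counts that loss as wins for the favoured arm

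*Combined protocol and SAP*

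**What the plan says.** Under section 9.4.2, a participant with no follow-up CGM data does not enter the primary model. The plan recruits 400 to retain 300, "which allows for up to 25% attrition"; it gives no split by arm. Two sensitivity analyses address such losses.

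- Multiple imputation of the missing outcome from baseline data.
- A win ratio. Death ranks worst and discontinuation for an adverse event second worst. Next, "participants that discontinued with no known adverse event are ranked as having the third worst outcome value". Participants with complete CGM data in the intensive period rank above all of these, ordered by % time below 54 mg/dl.

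The plan calls the win ratio an important check that a benefit on time below 54 mg/dl or on time-in-range (TIR) is among those that "are not offset or explained by greater death or discontinuation in the other treatment arm".

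**The concern.** The sentence names a specific threat: one arm looks better on CGM because the other arm lost more people. A useful check should weaken when that happens. This one strengthens, because the ranking treats a leaver as worse than anyone with complete CGM data. If control attrition helped to produce a glargine benefit, the win ratio would tend to agree and could be published as reassurance.

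The null hypotheses also differ. Section 9.1 tests whether glycemic outcome in the glargine group "is the same as % Time-in-serious hypoglycemia and % TIR in the control group". The win ratio tests equality of a ranking that mixes death, discontinuation and hypoglycemia, so it can reject when glycemia is identical.

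Unequal loss is conceivable here. The trial is open-label, and section 2.2 says that "many patients and global advocates strongly prefer newer insulins". The multiple imputation uses baseline data only, so it does not probe dropout that depends on the unseen outcome. That leaves the question of whether loss explains the benefit without a planned answer.

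**Working it through.** **Inputs from section 9.2.** Control % time below 54 is given as "mg/dl of 5.8, standard deviation of 6.6, a maximum of 24". The effect is a multiplier of 0.67, with 150 per arm analysed. On alpha, "an alpha threshold of 0.025 is used for each analysis to control the overall trial-wide type 1 error probability at 0.05". Power is "the percentage of simulated trials with a p-value less than 0.025 favoring glargine on each of the respective coprimary outcomes".

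**The plan's own figure.** Difference = 5.8 × 0.33 = 1.914. SDs are 6.6 and 6.6 × 0.67 = 4.42. SE = √[(6.6² + 4.42²)/150] = 0.649. Power = Φ(1.914/0.649 − 2.241) = Φ(0.71) = 76.1%, against the stated 77.7%. So the inputs, read as two-sided 0.025, are sound. Also 300/(1 − 0.25) = 400. The plan gives no figure for the win ratio.

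**Direction, from the ranking alone.** Move one control participant from the CGM tier to the no-known-adverse-event tier, and look at each pairing with a glargine participant:

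- Glargine participant with CGM data: the pair becomes a glargine win, whatever it was before.
- Glargine participant in the same discontinuation tier: a glargine loss becomes a tie.
- Glargine participant who died or left for an adverse event: still a glargine loss.

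No pairing moves against glargine. This holds whether or not dropout is related to glucose.

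**Size, closed form.** Assume no glycemic effect, dropout unrelated to glucose and a single discontinuation tier. Let dT and dC be the loss proportions for glargine and control.

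Wins = (1 − dT)dC + (1 − dT)(1 − dC)/2

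Losses = dT(1 − dC) + (1 − dT)(1 − dC)/2

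| Loss, glargine / control | Wins | Losses | Win ratio |
|---|---|---|---|
| 25% / 25% | 0.469 | 0.469 | 1.00 |
| 20% / 25% | 0.500 | 0.450 | 1.11 |
| 15% / 25% | 0.531 | 0.431 | 1.23 |
| 20% / 30% | 0.520 | 0.420 | 1.24 |

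**Simulation, loss unrelated to glucose.** Set-up: 200 per arm, gamma outcome with mean 5.8 and SD 6.6, no glycemic effect, assumed 1% deaths and 2% adverse-event discontinuation per arm, other losses in the third tier. The win ratio is significant for glargine (two-sided 0.05) in:

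- 2.5% of trials at equal 25% loss;
- about 13% at 20% vs 25%;
- about 39% at 15% vs 25% (median win ratio 1.22).

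False wins on time below 54 stay at 1.1–1.5%, against a nominal 0.025/2 = 1.25% in that direction.

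**Simulation, control leavers mainly those with low hypoglycemia.** With the chance of leaving falling linearly with the rank of time below 54, an unadjusted comparison gives a false win in about 22% of trials (20% vs 30% loss) to 37% (15% vs 35%). Repeat runs reached 26% and 41%. A milder mechanism (leavers 3:1 from the lower half) gives 14% and 19%. The win ratio exceeded 1 in all of these false wins and was significant in 98–100% of them.

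**The direction that works.** With a true 33% reduction, the win ratio is 1.23 at equal 25% loss, 0.99 at 30% glargine vs 20% control, and 0.80 at 35% vs 15%.

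**The case against.** **The wording may be a slip.** *Offset* makes sense only for losses in the arm that shows the benefit, and there the check works, as the fall from 1.23 to 0.80 shows. This stands, and it is why rewording is the main remedy. It does not rescue *explained*, which no reading of the ranking can deliver.

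**A reader might infer that the win ratio manufactures a glycemic benefit, or inflates the trial's error rate.** The documents do not support that. When dropout is unrelated to glucose, false co-primary wins stay near nominal, and a win ratio above 1 is a real difference on a composite that the plan openly describes as one and calls hard to interpret. It is a sensitivity analysis, so primary type I error is untouched.

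**A reader might also infer that the check can never disagree with a benefit.** That goes too far. It can disagree when the favoured arm loses more people, or when TIR improves while time below 54 worsens. The second case exposes a separate gap: TIR is not in the ranking, so the glycemic tier cannot check a TIR benefit.

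**The sizes rest on assumptions.** This stands. The plan gives no arm-specific attrition. Section 7.1 keeps participants who stop or switch insulin in follow-up and offers a switch at study end, which may help to retain controls. The informative scenario assumes selective loss in one arm only and omits the planned baseline covariates; with an assumed baseline–outcome correlation of 0.7, a false-win rate of 24% falls to 12%.

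**Conclusion.** The point holds in a limited form. The plan credits the win ratio with a property that its ranking does not have. Excess loss in the arm without the benefit can only push the win ratio towards the benefit, so agreement between the two says nothing about whether loss explains it. This follows from the ranking and needs no assumption. The percentages do depend on assumed arm-specific loss, a gamma outcome and, for false co-primary wins, loss related to glucose in one arm. With equal loss unrelated to glucose there is no distortion.

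The analysis remains valid for showing whether death or discontinuation in the favoured arm offsets a benefit. The text should be corrected before results are reported; the primary analysis is not in question.

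**What to change.** In section 9.4.2:

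1. Reword the sentence. Say that the win ratio checks whether excess death or discontinuation in the arm showing the benefit offsets that benefit. Remove *explained*. State that excess loss in the other arm raises the win ratio in favour of the benefit, and that the glycemic tier covers time below 54 only, not TIR.
2. Report wins, losses and ties by tier, with the by-arm difference in adverse-event and no-known-adverse-event discontinuation and its 95% CI.
3. Address the *explained* question by extending the planned multiple imputation with arm-specific delta-adjusted (tipping-point) imputation for both co-primary outcomes.

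A second win ratio that leaves no-known-adverse-event leavers unranked may be shown descriptively. It should not be a criterion for calling a co-primary win supported, because it drops the same leavers as the primary model. With glucose-related control loss it agreed with 100% of false wins on time below 54 and was significant in 91–97% of them.

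The cost is SAP wording and a little extra analysis of data already collected.

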#### 9.4.3 ANALYSIS OF THE SECONDARY ENDPOINT(S)

The secondary outcomes are: Time-in-hypoglycemia (<70mg/dl), time-above-range (either >180mg/dl or >250mg/dl), and number nocturnal hypoglycemic events (1200-0600h). We will also measure and compare overall glycemic control (HbA1c), the rate of severe hypoglycemic events (requiring the external assistance of another party), and the rate of symptomatic hypoglycemic events reported by clinical history, rate of diabetic ketoacidosis (measured by self-report and confirmed through review of hospital records) and overall mortality (all cause death).

We will also measure and compare quality of life using validated tools (PedsQL v3 and Insulin Treatment Satisfaction Questionnaire) at baseline and at 6 and 12 months after randomization. A minimum clinically important difference in QoL scores will be determined *a priori*. The primary treatment comparison for QoL will be made between the two treatment arms at 6 months after randomization.

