(especially overnight) when compared against human insulins (Pedersen-Bjergaard et al., *The Lancet Diabetes & Endocrinology* 2014). In fact, existing WHO treatment guidelines recommend considering long-acting insulin analogues in cases where patients experience recurrent episodes of hypoglycemia on human insulin (Roglic & Norris, *Annals of Internal Medicine* 2018).

The landscape of global access to medicine for patients living with insulin-dependent diabetes is undergoing a dramatic transformation. Clinics in low-resource settings supported by Life for a Child will soon begin transitioning some children and young adults with T1D from usual care with human NPH insulin to insulin glargine (Basaglar; Lilly/Boehringer Ingelheim). Given these changes, and existing gaps in the evidence, this is an opportune time to conduct a rigorous study that directly compares long-acting insulin analogues vs. human insulins (e.g., NPH or premixed 70/30 insulin) in low-resource settings. The overall goal of this project is to generate high-quality evidence on the potential clinical benefits and comparative cost-effectiveness of long-acting insulin analogues versus standard-of-care human insulin for patients living with T1D in these settings.

We will achieve this by conducting a randomized trial comparing glargine, a long-acting insulin analogue, against human NPH insulin or premixed 70/30 human insulin among 400 children and young adults living with T1D in lower resourced settings.

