### 8.2 SAFETY AND OTHER ASSESSMENTS

Study Measurements

Baseline demographics/comorbidities	Description
Age	At time of randomization, in years
Duration of type 1 diabetes	Based on self-report or extraction from medical record, in years
Type of insulin regimen	Generally, as two categories, NPH + regular (basal/bolus regimen) or premixed 70/30
Number of units of insulin per day	Total number of international units of insulin used per day, including all basal and bolus insulins.
Mean HbA1c (%) [SD]	HbA1c laboratory result (units=%), most recent
Complications of Type 1 Diabetes	Clinical presence or absence of diabetic retinopathy, neuropathy, or nephropathy (extracted from medical record)

Hypoglycemic events	Number of episodes of symptomatic hypoglycemic events in the past 12 months
Co-Primary Outcomes:	
Time-in-serious hypoglycemia	% spent less than 54mg/dl, averaged across all daily measures averaged across two CGM sensors starting 6 months after randomization
Time-in-range (TIR)	% between 70 and 180mg/dl inclusive, averaged across two CGM sensors 6 months after randomization
Secondary Outcomes:	
Time-in-hypoglycemia	% spent less than 70mg/dl
Time-above-range	% spent greater than 180mg/dl
Nocturnal hypoglycemic events	Number of events (defined as >=15mins in duration < 70mg/dl) between 1200 and 0600
Glycemic control (HbA1c)	Mean HbA1c lab result at baseline, 3, 6, 9 and 12 months after randomization
Rate of severe hypoglycemic events	Events requiring the assistance of an external third party person
Rate of diabetic ketoacidosis (DKA)	Measured by self-report and confirmed through review of hospital records
Quality of Life (e.g. Fear of Hypoglycemia Survey)	As assessed using validated instruments (PedsQL and Insulin Treatment Satisfaction Questionnaire (ITSQ)).
Adverse Events	
Hypoglycemic events (clinically significant events)	See primary and secondary outcomes above. Insulin in any form is known to be associated with low blood sugars. Therefore, we are measuring this as a primary/secondary outcome...but it also may be considered an adverse event/safety event.
Severe hypoglycemic events (<54mg/dl by CGM) > 10%	In the case severe hypoglycemia exceeds 10% on any CGM sensor, the treating clinician will be notified.
Skin discomfort/irritation	Self-report
Skin infection	Self-report

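### The nocturnal hypoglycemia outcome is written with a noon-to-06:00 window and as a raw count, although nights of sensor data will differ between participants

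*Combined protocol and SAP*

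**What the plan says.** The outcome is defined in three places, all with the same clock times.

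- Section 9.4.3 lists the "number nocturnal hypoglycemic events (1200-0600h") among the secondary outcomes. Section 3 uses the same expression.
- The outcome table in Section 8.2 gives the fuller definition: "Number of events (defined as >=15mins in duration < 70mg/dl) between 1200 and 0600".

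None of the three gives a per-night or per-week denominator, a minimum number of nights, or the sensors to be counted. Section 9.4.3 gives no model for this outcome. In the same paragraph it describes severe hypoglycemia, symptomatic hypoglycemia and ketoacidosis as rates.

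The clinical reason for the outcome is in Section 2.2. NPH has a peak "which can lead to hypoglycemia if not eating or overnight", glargine "may reduce the risk of severe hypoglycemic events overnight, which can be fatal", and the preference for newer insulins is linked to fewer hypoglycemic events ("especially overnight) when compared against human insulins").

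Section 9.4.2 covers incomplete sensor data. For a sensor that falls off early, fails to download or is accidentally removed before 9.8 days, participants "they may receive a replacement sensor". If the sensor is worn for the full 14 days but "a sensor shuts-off early (e.g. only 6 days of glucose measurement data is captured), they will not have a replacement sensor". The primary analysis uses all sensor data "regardless of the duration of sensor wear or the number of days of glucose measurements". The stated rationale is that random allocation should even out incomplete recordings between the arms.

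**The concern.** There are two faults in one outcome definition.

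**The window.** The notation is 24-hour, so 1200 is noon. A window from noon to 06:00 takes in the afternoon and evening, which fits neither the label nocturnal nor the overnight rationale in Section 2.2. Because all three places agree, there is no correct version for a programmer to fall back on. If the window were programmed as written, daytime and evening events would be counted as nocturnal, and an effect confined to the night would be diluted.

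**The denominator.** A number of events grows with the number of nights recorded. The other CGM outcomes are percentages of time and so are already scaled to recorded time. This one is not, and the plan itself expects recordings of unequal length. Two participants with the same nightly event rate would then have different outcome values.

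**Working it through.** The plan gives no sample size, power or alpha for this outcome. Its one related figure, the 70% data threshold in Section 9.4.2, reproduces: 0.70 × 14 = 9.8 days.

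**Window length** (clock times from Sections 3, 8.2 and 9.4.3)

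| Reading | Hours | Share of day |
|---|---|---|
| 1200 to 0600 as written | 12 + 6 = 18 | 18/24 = 75% |
| 0000 to 0600 | 6 | 6/24 = 25% |

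The written window is 18/6 = 3 times as long as the midnight one, and 12/18 = 67% of it lies before midnight. How far an overnight effect would be diluted cannot be calculated. The documents give no hourly event rates, and Section 2.2 also links NPH hypoglycemia to not eating, so an effect outside the night is possible.

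**Nights observed.** Inputs: 14 days per sensor and two sensors at 6 months (Section 3); a 6-day recording as the plan's example of a short sensor (Section 9.4.2). Assumption: this outcome uses the same two sensors as the co-primaries, giving 2 × 14 = 28 nights.

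- One 6-day and one full sensor: 6 + 14 = 20 nights. At an equal event rate the count is 20/28 = 71% of a full count.
- If the 70% rule were applied here, a sensor could still hold 9.8 to 14 days: 14/9.8 = 1.43-fold.
- If partial and replacement data were both kept, a sensor removed at day 9 and replaced in full, plus a full second sensor, gives 9 + 14 + 14 = 37 nights against 28.
- If all four follow-up sensors in Section 3 were counted (one at 3 months, two at 6, one in month 12), the full count is 4 × 14 = 56 nights. One 6-day sensor then gives 48/56 = 86%.

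**Size of the noise.** The documents do not give the share of short recordings. Assume a share p has 20 nights and the rest 28. The mean is 28 − 8p and the SD is 8√(p(1−p)), so

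CV of nights = 8√(p(1−p)) / (28 − 8p)

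| Assumed p | Calculation | CV |
|---|---|---|
| 0.10 | 2.40 / 27.2 | 8.8% |
| 0.20 | 3.20 / 26.4 | 12.1% |
| 0.40 | 3.92 / 24.8 | 15.8% |

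For scale, Section 9.2 gives time below 54 mg/dl a mean of 5.8 and an SD of 6.6, a CV of 6.6/5.8 = 114%. Take that as a rough stand-in for the spread of event rates between participants (an assumption, since it is a different measure). If nights vary independently of the rate, the CV of the count is √((1 + 1.138²)(1 + CV²) − 1). This is 114.6% at CV = 8.8% and 116.3% at CV = 15.8%, a rise of about 0.7% to 2.2% in relative SD.

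**The case against.** The strongest reply is that the window is a slip nobody would follow. The label and the overnight rationale rule out a noon start, so the 75% and 67% figures describe a reading that no one intends. That is fair as to likely harm. It does not remove the fault. The slip sits inside an outcome definition, appears every time the outcome is defined, and in an open-label trial should not be left for reinterpretation once data are in hand. The reply is also right that the documents exclude noon without stating the true start hour, so the sponsor must confirm it.

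On the denominator, it can be said that the word number only names what is measured, that no section says totals will be compared regardless of recorded time, and that Section 9.4.3 gives no model for any CGM secondary outcome. The inclusion rules in Section 9.4.2 are written for the co-primary analyses, so carrying them over is an inference. Both points stand as limits. Even so, neighbouring event outcomes are called rates and this one is not, and the same sensors supply its data.

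Finally, the noise is small, the assumed shares come from outside the plan, and nothing in the documents suggests that wear differs by arm. This is accepted. Balance through random allocation answers the question of expected bias. It does not remove the variation between participants, and it does not make an unscaled count easy to interpret.

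**Conclusion.** The concern holds and is minor. The window is wrong as written in all three places: 18 hours from noon, where 6 hours from midnight was very probably meant. That reading is an inference from the label and the rationale. The count has no denominator although unequal recording is expected: 20 of 28 nights, or 71% of a full count, in the plan's own example of a short sensor, assuming the two 6-month sensors are the ones counted.

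Unequal nights add modest noise, with a CV of nights of about 9% to 16% if 10% to 40% of participants have one short sensor (assumed shares). They would add bias only if recorded time differed by arm, which the documents do not suggest. No dilution figure can be given for the window. The co-primary outcomes, alpha and power are untouched.

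**What to change.** - Confirm the intended window, evidently 0000 to 0600 local time, and correct it in Section 3, the Section 8.2 table and Section 9.4.3.
- Define the outcome as events per night of CGM data. The choice of count model can be left to the trial statistician; a log-nights offset would achieve the same scaling.
- In the same edit, name the sensors counted, for example the two 6-month sensors used for the co-primary outcomes.

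The cost is wording in three places and division by nights of data in the analysis program. No new data or visits are needed. The change should be made before the outcome is analysed.
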